### **Analytical Plan**

We will use an analysis of variance model for crossover design to assess the effect of metformin on transcriptional profiles and other aging-related outcomes. The factors in the analysis will include the baseline measure, sequence, participant within sequence, period, and metformin treatment. We will explore for the metformin by sequence interaction and will base estimates of the metformin effect on whether this interaction effect is significant. We will also perform exploratory, linear regression analysis with transcriptional changes as the explanatory variables and changes in other aging-related measures as the outcome variables. The analysis will be focused on the eigengene scores of the autophagy and oxidative phosphorylation transcriptional networks (and related individual transcriptional measures). As this is a pilot study, focus of analyses will be on estimation of effects and constructing appropriate 95% confidence intervals for these effects.

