### **Objectives**

Our overarching goal of the pilot study is to evaluate the utility of using the aging-related omic biomarkers as an indicator of pharmacologic responses in the anti-aging therapeutic intervention trials through the following specific aims. Although this pilot study does not have sufficient power to definitively test all the aims, it will provide essential preliminary data for developing a full scale research program.

- Aim 1A: To test the effects of the metformin treatment on transcriptomic profiles and related functional changes in human monocytes,
- Aim 1B: To explore the effects of the metformin treatment on methylomic profiles in human monocytes,
- Aim 2: To investigate the longitudinal relationship between transcriptional and functional changes in human monocytes during the metformin treatment and
- Aim 3: To test the effects of the metformin treatment on frailty and other aging-related physical and cognitive measures and investigate the longitudinal relationship between these changes and transcriptional changes.

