#### **Schedule and organization of assessment visits**

All assessments will be conducted during 4 visits (before and after each intervention) according to the chart below. All examiners are trained in the standardized conduct of all assessments before data collection. Participants will be instructed to wear appropriate and comfortable clothing, and standardized written instructions will be provided prior to each study visit.

Assessment timeline	Visit code	SV	BV	On trial	Mid	On trial	FV
Activity/assessment	Week number	-4	0		12-14		24-26
Informed consent, review inclusion/exclusion criteria, demographics, weight, height, BP and pulse, fasting screening blood draw (metabolic blood panel, lipid panel, CBC, Vit B12, Hba1c), eSPPB, cognitive screen (MoCA), waist circumference, medical history, medications PAT-D,		X					
Blood collection for methylomic and transcriptomic, bioenergetic capacity, CBC, and blood for storage, DSST, leg press, grip, MATsf, and 6MWD			X				
Randomization			X				
Crossover – Dispense New Medication					X		
Vitals, blood collection for methylomic and transcriptomic, bioenergetic capacity, and blood for storage, CBC, CMP, lipids, Hba1c, eSPPB, MoCA, DSST, leg press, grip, PAT-D, MAT-sf, 6MWD					X		X
Health Maintenance							X

The screening visit (SV) will be conducted in the morning following an 8-hour fast for measurement of lipids, blood count, Hba1c, Vitamin B12, and a metabolic panel for screening purposes. Vitals (blood pressure, pulse, height, weight, and waist circumference) are collected and the blood draw completed, participants will be given a snack and continue with the remainder of the visit. First, the expanded short physical performance battery (eSPPB) will be administered and scored and then undergo a cognitive screen, assessed using the Montreal Cognitive Assessment (MoCA), and a medical history, review of medications and dietary supplements. We will also ask about the participants demographics and physical abilities using the Pepper Assessment Tool for Disability (PAT-D),

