The first baseline visit (BV), will be conducted in the morning following an 8-hour fast for blood collection for methylomic and transcriptomic measures, bioenergetic capacity, CBC, as well as blood for storage. After these measures are complete, participants will be given a snack and will continue with the rest of the visit consisting of lower extremity muscle power (Nottingham Power Rig), grip strength, 6 minute walk distance test (6MWD), and the Mobility Assessment Tool – short form (MAT-sf). Cognitive function will be assessed using the Digit Symbol Test (DSST). Once the visit is complete, the participant will be randomized and placed in one of the following groups discussed below. Participants will be provided with an information sheet that will provide additional details on how and when to take the medication, who to call if they have any problems, possible side effects, and what to do should they encounter any side effects.

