#### Interventions and Interactions

Eligible participants will receive both interventions (3-month metformin treatment and 3-month placebo). Randomization will be used to determine the order in which the participants receive each intervention (i.e., 15 participants with metformin treatment followed by placebo, and 15 with placebo followed by metformin treatment). Neither the participants nor the investigators know the intervention order of a participant. Metformin reaches peak plasma concentration within one to eight hours, has an average elimination half-life of 6.2 hours in plasma, and is cleared but not metabolized from the body by tubular secretion. Treatment with metformin and placebo will be initiated at a dose of 425 mg taken orally once a day at night for 7 days. After the week, the participant will be called to assess tolerance and will be asked to increase dose to one pill at night at a dose of 850 mg for one week. At the end of the second week, participants will be called again and if they tolerated the second dose, they will be asked to take two 850mg pills, one in the morning and one at night, for a total dose of 1700 mg which is within the range of the usual effective dose of 1500 to 2000 mg/day for the remainder of the 3 months. This dosing regimen was created in order to avoid or reduce possible gastrointestinal side effects. This can be modified if the

participant is experiencing any side effects and will be handled on a case by case basis. Each study visit where stored blood is obtained (BV, Mid, FV) may be rescheduled if the subject has a fever, infection, or has taken antibiotics within 24hrs of this scheduled visit.

All baseline assessments will be completed again at 12 weeks and again at 24 weeks as listed in the assessment table.

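### Does leaving the baseline visit unnamed in the crossover model put the metformin estimate at risk?

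*Combined protocol and SAP*

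**What the plan says.** The model in the Analytical Plan is an analysis of variance for a crossover design: "The factors in the analysis will include the baseline measure, sequence, participant within sequence, period, and metformin treatment". The baseline is in the singular and no visit is attached to it. The same section says the "focus of analyses will be on estimation of effects and constructing appropriate 95% confidence intervals for these effects".

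Two places bear on which visit is meant, and they point in different directions.

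- Schedule and organization of assessment visits: "All assessments will be conducted during 4 visits (before and after each intervention) according to the chart below". The chart lists SV, BV, Mid and FV, with "Crossover – Dispense New Medication" in the Mid column. The text below it begins: "The first baseline visit (BV), will be conducted in the morning following an 8-hour fast".
- Interventions and Interactions: "All baseline assessments will be completed again at 12 weeks and again at 24 weeks as listed in the assessment table".

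Blood for the omic outcomes is drawn at BV, Mid and FV only. The chart collects eSPPB, MoCA, PAT-D, lipids and HbA1c at SV, Mid and FV.

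**The concern.** The second-period drug is handed out at Mid, so Mid is the end-of-period-1 outcome and no untreated baseline exists for period 2. The remark about assessing before and after each intervention, and the word *first* attached to the baseline visit, could lead an analyst to take Mid as a second baseline. In the metformin-first sequence that value follows three months of metformin. In the other sequence it follows three months of placebo. Adjusting for it would remove or add part of the effect being estimated.

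The estimate and its interval are what this pilot is meant to deliver. The Objectives say that "it will provide essential preliminary data for developing a full scale research program". A biased effect size would carry over into the planning of the next trial: at equal SD, a sample size based on 0.75 of the true effect is 1/0.75² = 1.78 times the right one.

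**Working it through.** The plan gives no effect size, SD or correlation, so there is no figure of its own to reproduce. The check uses algebra and simulation.

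**Inputs.** From the documents: outcomes at BV, Mid and FV; 15 participants per sequence (Interventions and Interactions; the Design section says 35 in total); the model terms quoted above; 95% intervals. Assumed: unit SD at every visit, complete data, no carryover at FV, correlation ρ between visits, true effect τ in SD units.

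**Reduction.** With participant as a fixed factor, the model is a regression of D = FV − Mid on sequence and on the change in the baseline covariate between periods. Write π for the period effect. The mean of D is π − τ for metformin-first and π + τ for placebo-first, so half the difference between sequences is τ.

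**BV as baseline in both periods.** The covariate change is 0 for everyone, so the baseline term drops out and the expected estimate is τ.

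**Mid as the period-2 baseline.** The covariate change is Mid − BV. Its mean is higher by τ in the metformin-first sequence. With fitted slope β,

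E(estimate) = τ − β(0 − τ)/2 = τ(1 + β/2).

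Here β is the within-sequence slope of FV − Mid on Mid − BV:

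- Equal correlation: β = −(1 − ρ)/[2(1 − ρ)] = −0.5, so the estimate is 0.75τ for any ρ.
- AR(1): β = −(1 − ρ)²/[2(1 − ρ)] = −(1 − ρ)/2. At ρ = 0.5, 0.7 and 0.9 the estimate is 0.875τ, 0.925τ and 0.975τ.

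**Simulation, 15 + 15, participant fixed:**

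| Period-2 baseline | Correlation | τ | Mean estimate | Coverage of 95% CI |
|---|---|---|---|---|
| BV | equal, 0.7 | 0.5 | 0.50 | 95% |
| Mid | equal, 0.7 | 0.5 | 0.38 | 85% |
| Mid | equal, 0.7 | 0.3 | 0.23 | 91% |
| Mid | equal, 0.7 | 0.2 | 0.15 | 93% |
| Mid | equal, 0.7 | 0 | 0.00 | 95% |
| Mid | AR(1), 0.7 | 0.5 | 0.46 | 94% |

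**Scale of the worst row.** At ρ = 0.7 the within-participant SD is √(1 − 0.7) = 0.548, so τ = 0.5 is 0.5/0.548 = 0.91 within-participant SD. That is a large effect for a pilot which says it lacks power to test all its aims definitively.

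**Bias against sampling error.** With BV, the variance of the estimate is ¼ × (0.6/15 + 0.6/15) = 0.02, where 0.6 = 2(1 − 0.7). The SD is 0.14. The unbiased estimate of 0.5 therefore ranges over about 0.5 ± 1.96 × 0.14, or 0.22 to 0.78. The shift to 0.375 lies well inside that range.

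**Which reading the text supports.** BV is the only visit called a baseline visit. Interventions and Interactions treats the week-12 and week-24 assessments as repeats of baseline. The four visits in the Schedule section are SV, BV, Mid and FV. One of the four is therefore screening, and the parenthesis about before and after is a loose description that names no covariate.

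**The case for a change.** The strongest opposing case is that the text does not exclude Mid. If participant is fixed, a BV covariate does nothing, so a reader may ask why a baseline term is listed unless it varies by period. The plan also does not say whether participant is fixed or random. With a random intercept and Mid as covariate the bias reverses, to 1.15–1.45τ for correlations of 0.3 to 0.9. One sentence would settle the matter at no cost, and leaving it open allows the choice to be made after the data are seen.

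The algebra stands, and so does the absence of a named visit. The rest carries less weight. A redundant baseline term in a list of model factors is common and harmless; if participant is random, the BV term is still unbiased. The inflated figures need two choices the plan does not state: Mid as covariate, and a random-participant model in place of the analysis of variance it names.

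For measures not taken at BV, the chart leaves only the screening value as a pre-randomisation baseline. A similar worry applies to the exploratory "linear regression analysis with transcriptional changes as the explanatory variables and changes in other aging-related measures as the outcome variables", where the plan does not say how changes are formed. A false association arises there only under particular ways of pooling the two periods, and the plan does not adopt any of them.

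**Conclusion.** The concern describes a real error that an analyst could make, but the plan does not make it. With the natural reading (the pre-randomisation value, from BV or from SV where the chart has no BV measurement) the metformin estimate is unbiased and its interval has 95% coverage.

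The harm requires Mid to be used as a covariate. Even then, with participant fixed, it is zero when metformin has no effect, small under serial correlation (0.925τ and 94% coverage at AR(1) 0.7), and material for the interval only when a larger effect meets equal correlation (0.75τ and 85% coverage at 0.5 SD). These sizes rest on assumed correlations and effects, complete data and no carryover at FV.

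What remains is missing detail in a short pilot plan. Analysts may note the baseline visit in their programming specification, but no change to the plan follows.

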**Exclusion Criteria**

eGFR <45  
Type 2 diabetes (HbA1c>6.5) or type 1 diabetes  
Any tobacco or nicotine product use in the past year  
Low vitamin B12 Levels (< 300 pg/mL)  
Self-reported severe difficulty or inability to walk 400m or climb 10 steps (from Q 2 and 19 on PAT-D)  
Self-reported difficulty or inability to perform basic ADL functions (from Q 10, 13, 14, 16 on PAT-D)  
Excessive alcohol use (>14 drinks/week)  
Cancer requiring treatment in past year (except skin)  
Dementia – diagnosed and/or MoCA score <18  
Parkinson's or other neurological disease  
Chronic liver disease or cirrhosis  
End stage renal disease or on dialysis  
Rheumatic conditions (Rheumatoid arthritis, lupus, and any other autoimmune disease the PI deems them to be ineligible for)  
Thyroid problems the PI deems them to be ineligible for  
Recent or recurrent exacerbation of gout  
Involved in another interventional study  
Hemoglobin  $\leq$ 8 or diagnosed with anemia  
Recent unintentional weight change (+/- 10 lbs. in the last 12 months)  
BMI <18.5  
Likely to not follow the protocol  
PI deems unfit to participate  
Already taking Metformin or any other drug intended to treat diabetes

***Screening, consent and randomization.*** Individuals who pass the telephone screening will be scheduled for a visit to the Geriatric Research Clinic (GRC) in the Sticht Center on Aging for a screening visit (SV). Before any data collection, all participants will provide written informed consent and complete a HIPAA authorization form in accordance with the Wake Forest School of Medicine Institutional Review Board policies. Individuals who meet all eligibility criteria and provide informed consent will be invited back for the first baseline visit (BV). At the end of BV, participants will be randomized to one of the two study intervention sequences (metformin followed by placebo or placebo followed by metformin) using a web-based randomization scheme (developed by [name]). The randomization sequences will be unknown to the research staff. Intervention assignment will be generated using a program that the study coordinator will access from his/her PC through the study website.

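### The metformin estimate is selected by a metformin-by-sequence test that duplicates the period term or, if carry-over is meant, is an unspecified pre-test that costs confidence-interval coverage

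*Combined protocol and SAP*

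**What the plan says.** The Analytical Plan specifies an analysis of variance for a crossover design: "The factors in the analysis will include the baseline measure, sequence, participant within sequence, period, and metformin treatment". It continues: "We will explore for the metformin by sequence interaction and will base estimates of the metformin effect on whether this interaction effect is significant". It gives no significance level, no test procedure, and no estimate to report if the interaction is significant. The same paragraph makes estimation with 95% confidence intervals the focus of this pilot.

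The Design section makes absence of a treatment-by-sequence interaction the condition for the within-participant gain, and discusses the period effect separately as likely to be minimal. Under Screening, consent and randomization, "participants will be randomized to one of the two study intervention sequences (metformin followed by placebo or placebo followed by metformin").

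The baseline in the model is not identified. The visit schedule says: "All assessments will be conducted during 4 visits (before and after each intervention) according to the chart below". The chart, however, has no separate measurement between the two treatments: the Mid visit (weeks 12-14) collects the period-1 outcomes and also carries the entry "Dispense New Medication". Interventions and Interactions adds: "All baseline assessments will be completed again at 12 weeks and again at 24 weeks as listed in the assessment table". No washout is described; that section does state that metformin "has an average elimination half-life of 6.2 hours in plasma".

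**The concern.** The main product of the trial is a metformin effect with a 95% interval for each outcome, and the plan lets a significance test decide which estimate that is. There are two difficulties.

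- **Literal reading.** The tested term duplicates a factor already in the model, so the rule cannot be carried out. If period is removed so that the term can be fitted, the rule becomes a test for a period effect. A period effect does not bias the period-adjusted contrast and is no reason to abandon it.
- **Carry-over reading.** The rule is a two-stage procedure. Its pre-test is weak and is correlated with the obvious fallback, the period-1 comparison, so the reported interval is not a 95% interval even when there is no carry-over.

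In either case, two analysts could report different estimates from the same data. The undefined baseline adds a third route to divergence, because the Mid measurement could be entered as a period-2 covariate although it is the period-1 outcome.

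**Working it through.** **Inputs from the document.** Two sequences and two periods; the model terms listed above; nominal 95% intervals; 35 participants (Design) or 15 + 15 (Interventions and Interactions). These sizes disagree, so 15/15 and 17/18 were both examined.

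**Assumptions not in the document.** Outcomes scaled to SD 1; equal correlation ρ between BV, period 1 and period 2 (0.5 / 0.8 shown, 0.3 to 0.9 examined); true effect 0.5 SD; pre-test at 5% or 10%; the fallback; the sizes of period shift and carry-over.

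**1. Duplication (no assumptions).** Code sequence s = ±1 and period p = ±1, with +1 for metformin-first and for period 1. Treatment is then t = s·p, so t·s = s²·p = p. Model rank without a baseline:
- 15/15: 1 (intercept) + 1 (sequence) + 28 (participants) + 1 (period) + 1 (treatment) = 32
- 17/18: 1 + 1 + 33 + 1 + 1 = 37

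Adding treatment × sequence leaves 32 and 37. A BV covariate is constant within participant and changes nothing; a period-specific covariate gives 33 to 33 and 38 to 38.

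**2. The nominal 95%.** The unconditional within-participant contrast, with no carry-over, has simulated coverage of 95.1% (15/15) and 95.0% (17/18).

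**3. Carry-over reading, period-1 fallback, no true carry-over.** The pre-test uses participant totals Y1 + Y2. Its correlation with the period-1 estimate is √((1+ρ)/2), which is 0.87 / 0.95. The crossover contrast Y1 − Y2 is uncorrelated with the total. So:

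coverage ≈ 0.95 × 0.95 + 0.05 × (coverage of the period-1 interval when the test fires)

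That conditional coverage is about 49% / 30% unadjusted, giving 0.9025 + 0.0245 = 92.7% and 0.9025 + 0.015 = 91.8%. Simulation at 15/15 agrees:

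| Pre-test level | Unadjusted, ρ 0.5 / 0.8 | BV-adjusted, ρ 0.5 / 0.8 |
|---|---|---|
| 5% | 92.7% / 91.7% | 93.0% / 92.7% |
| 10% | 91.9% / 90.9% | 92.2% / 92.0% |

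Over ρ = 0.3 to 0.9 and both sample sizes the full range is 90.7 to 93.3%.

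**4. What the pre-test buys.** Carry-over λ in period 2 of metformin-first biases the crossover estimate by −λ/2. Results at 15/15 for ρ 0.5 / 0.8, with the BV-adjusted 5% test:

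| λ | Test fires | Gated coverage | Fixed crossover coverage |
|---|---|---|---|
| 0.25 SD | 7% / 10% | 88% / 81% | 90% / 82% |
| 0.5 SD | 15% / 24% | 76% / 56% | 74% / 45% |

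The BV-adjusted period-1 interval, always reported, stays at about 95%.

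**5. Literal reading with period dropped, 5% test, 15/15.** The gate fires 5% / 5% with no period shift, 8% / 13% at 0.1 SD, 19% / 39% at 0.2 SD and 36% / 71% at 0.3 SD.
- *Period-1 fallback:* coverage stays near 95%, because with equal groups the period contrast is uncorrelated with the period-1 comparison. The cost is precision. The crossover half-width is t × ½√(2(1−ρ)) × √(2/15), about 0.37 / 0.23 SD. The adjusted period-1 half-width is about t × √(1−ρ²) × √(2/15), or 0.65 / 0.45 SD.
- *Sequence-specific fallback:* with period shift π the two sequences estimate τ − π and τ + π. Under the gated rule, coverage of the metformin effect τ is 93% / 91%, 89% / 81% and 82% / 61% at shifts of 0.1, 0.2 and 0.3 SD.

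**6. Mid as period-2 baseline.** With participants fixed, the covariate enters as BV − Mid, and Mid is Y1. The within-sequence slope of Y1 − Y2 on BV − Y1 is (ρ − 1)/(2(1 − ρ)) = −½ for any ρ. Between sequences, Y1 − Y2 differs by 2τ and BV − Mid by −τ, so the adjusted estimate is ½(2τ − τ/2) = 0.75τ. A true 0.5 SD is estimated as 0.375 SD, with simulated coverage of 89% / 80%.

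**The case against.** The strongest reply is that carry-over was plainly intended. The Design section separates the interaction from the period effect, and the listed factors (sequence, participant within sequence) allow the carry-over test to be computed. On that view the literal reading is a slip of terminology, and the figures with period dropped describe a model that the plan does not specify. This largely stands. Step 5 shows only what follows if an analyst makes the written term estimable, and on that route a period-1 fallback costs width rather than coverage.

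The coverage loss of 2 to 4 points depends on an assumed fallback and test level. That also stands, but the plan names neither, and every setting examined fell below 95%.

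A fixed crossover estimate is not always better. With 1 SD of carry-over it covers 25% / 1%, against 56% / about 70% for the BV-adjusted 5% gate, and a short plasma half-life does not show how long transcript or methylation changes last. However, 1 SD is twice the assumed treatment effect, and neither rule is adequate there. This is the reason to show the period-1 estimate every time.

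Finally, the plan says baseline measure in the singular, so use of Mid is a possible misreading rather than a stated intention. That is fair; one sentence would exclude it.

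**Conclusion.** The concern holds. That the written interaction equals the period term is algebra and needs no assumption. On the more likely carry-over reading, the rule is an unspecified pre-test. With a period-1 fallback and no carry-over, its intervals cover about 91 to 93% instead of 95%, and it gives little protection against moderate carry-over. The exact loss depends on the assumed correlation, test level and fallback, none of which the document supplies. The baseline ambiguity is secondary: if Mid were used, the effect would be attenuated by 25%.

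This should be fixed before analysis, because it governs the estimate that the pilot exists to provide. It is a matter of analysis wording in an estimation-focused pilot and does not threaten the trial.

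**What to change.** In the Analytical Plan, delete the conditional sentence and state:

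- *The metformin effect for every outcome is the within-participant contrast from the model with sequence, participant within sequence, period and treatment, whatever the sequence or period test shows.*
- *Any baseline covariate is the pre-randomisation value: BV, or SV for measures taken before randomisation only at SV (such as eSPPB, MoCA and PAT-D). Mid is not a period-2 baseline, because it is the period-1 outcome.* A BV covariate leaves the within-participant estimate unchanged; it sharpens only the sequence contrast and the period-1 estimate.
- *The estimate assumes negligible differential carry-over; no washout is described.* The 6.2-hour plasma half-life and the roughly 12 weeks before the period-2 outcome support this assumption but do not prove it.
- *The sequence (carry-over) contrast with its interval and the baseline-adjusted period-1 estimate are always reported as sensitivity results and never select the primary estimate.*

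In the Design section, replace treatment by sequence interaction with differential carry-over.

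The cost is wording only; all the sensitivity results use data already planned. The downside is somewhat lower coverage than the gated rule if carry-over is large (74% / 45% against 76% / 56% at 0.5 SD), which the always-reported period-1 estimate would help to expose.
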